4.2 Randomization and Treatment Assignment

Up to 1200 planned subjects will be randomized to receive either roxadustat or placebo in a double-blind manner, resulting in approximately 800 subjects receiving roxadustat and approximately 400 subjects receiving placebo.

Randomization is stratified by the following factors:

- Screening Hb values (≤ 8 g/dL vs > 8 g/dL)
- History of cardiovascular, cerebrovascular or thromboembolic diseases (Yes vs No)
- eGFR (< 30 mL/min/1.73 m² vs ≥ 30 mL/min/1.73 m²)
- Geographic region (US vs Ex-US).

Randomization schedules will be prospectively prepared. Automated randomization and treatment assignments will be provided by an Interactive Response System (IWRS).

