5.4 ADDITIONAL DATA HANDLING RULES AND PRESENTATION SPECIFICATIONS

The following general guidelines will apply to all statistical analyses and data presentations:

- Baseline is defined as the last available value obtained prior to the first dose of study drug, unless otherwise specified in this SAP.
- Hb baseline is defined as the mean of the last four available values obtained prior to the first dose, including the Day 1 pre-dose value.
- eGFR and urine albumin-to-creatinine ratio (UACR) baseline will use the mean of all available central lab values prior to the first dose of study drug, including the Day 1 pre-dose value.
- Baselines for reticulocyte count, reticulocyte hemoglobin content (CHr), hepcidin, hs-CRP, serum iron parameters (transferrin, TIBC, TSAT, Ferritin, sTfR, and iron), blood pressures and heart rate are defined as the mean of values obtained within two weeks prior to the first dose.
- Randomization stratification factors derived from actual data (not the ones from the randomization system) will be used in all applicable analysis models. A table will show the discrepancies between the two.
- Analysis visits (instead of the nominal visits from CRF) derived from visit dates and visit time windows will be used in all analyses, tables, listings and figures. Unscheduled visits within an allowable window will be grouped into the closest scheduled visits based on the visit window specified in Appendix 1. For subjects who have more than one measurement at a scheduled visit, the last measurement will be used, with the exception of CPK, WBC, liver function tests (i.e., ALT, AST, GGT, ALP, and total bilirubin), in which the maximum measurement will be used.

- By default, US conventional units will be used for laboratory value presentations. A set of lab summary tables in SI units will also be provided based on TLF index.
- Age is calculated as of date that the informed consent form was signed.
- age = INTCK('YEAR', Birth Date, Date of Informed Consent, 'C')
where INTCK is a SAS function.
- Duration of treatment or days in treatment is calculated as: last dose date – first dose date +1
- Body weight, height and temperatures will converted using the following formula:
 - kg = lb/2.2
 - cm = 2.54 x in
 - C° = (5/9) x (F° – 32)
- eGFR will be calculated using the following Modification of Diet in Renal Disease (MDRD) equation:

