12.1 PRIMARY ANALYSIS

For US (FDA) Submission

The primary US FDA efficacy endpoint will be analyzed using the ITT population as the primary analysis population.

The primary efficacy endpoint for the US (FDA) submission is the Hb CFB to the average level during the evaluation period, defined as Weeks 28 to 52.

The rationale for choosing the specified evaluation period as the primary endpoint for US (FDA) submission is that one would expect to have achieved Hb correction by Week 28, and averaging it to Week 52 would be an accurate reflection of a longer term therapeutic effect of roxadustat.

The hypothesis to be tested for the primary efficacy analysis is:

H_0 : Hb CFB to the average of Weeks 28 to 52 in the roxadustat group = Hb CFB to the average of Weeks 28 to 52 in the placebo group

Versus:

H_1 : Hb CFB to the average of Weeks 28 to 52 in the roxadustat group \neq Hb CFB to the average of Weeks 28 to 52 in the placebo group

The efficacy endpoint will be defined as each patient's Hb change from baseline to the average level during the evaluation period, defined as Week 28 to 52 of the treatment period. A Multiple Imputation Analysis of Covariance model (MI ANCOVA) will be used to test the primary hypothesis. The model will contain terms for baseline Hb and baseline eGFR measurements as covariates and treatment arm and the other randomization stratification factors except screening Hb (≤ 8 vs > 8) and eGFR factor as fixed effects.

The MI ANCOVA model will be used to compare the pooled roxadustat and pooled placebo groups: Pooled roxadustat (TIW+BIW+QW) vs. pooled placebo. Efficacy by maintenance dosing frequency (i.e., TIW, BIW, QW vs. pooled placebo) will also be evaluated using FAS.

H_0 will be tested at the two-sided alpha = 0.05 level of significance and will be rejected if the $p < 0.05$ from the test.

The following steps will be used to conduct the primary analysis.

1. Generate 200 datasets, using seed 126345, where intermittent missing hemoglobin data will be imputed for each treatment relying on non-missing data from all subjects within each treatment group using the Monte Carlo Markov Chain MCMC imputation model with treatment, baseline hemoglobin, randomization stratification factors, and the available non missing hemoglobin for each scheduled Week.

The MCMC statement in the SAS PROC MI procedure with monotone option will be used. As a result, each dataset will only have missing ending data, or a monotone missing data pattern.

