Sample SAS code:

```
PROC MI data=xx out=xx seed=xx nimpute=200;
  by treatment;
  var treatment covariates Week1 ... Week 52;
  mcmc impute=mono;
run;
```

2. For each dataset from step 1, missing ending data (hemoglobin up through end of evaluation period) will be imputed using seed 472794. As a result, 200 imputed complete datasets will be generated.
 - Missing data at Week 1 will be imputed using the regression imputation model with baseline stratification factor, baseline and hemoglobin from Week 1, using the SAS PROC MI procedure with the REGRESSION option in the MONOTONE statement.

- The SAS PROC MI procedure will use data separately from each treatment subject to impute the missing data for a specific Week (i.e., only those that need the imputation for the Week). Since subjects from the different treatment groups for that Week are excluded from the step, they will not contribute to the imputation for the Week.
- Repeat for all other scheduled Weeks sequentially (Week 2 to the end of evaluation period). Subjects whose missing data were imputed for previous Weeks will contribute to the imputation for the current Week.

The regression imputation model includes an intercept and the slopes of the hemoglobin from previous Weeks and the stratification factors.

3. Analyze each imputed dataset using the analysis of covariance model (ANCOVA) using the mean of all observed or imputed Hb values within the evaluation period. The model will contain terms for baseline Hb and eGFR measurements as covariates and treatment arm and the other randomization stratification factors except baseline Hb (≤ 8 vs > 8) and eGFR as fixed effects.

Sample SAS code:

```
PROC MIXED data=xx;  
  class treatment categorical covariates;  
  model change_Week36 = treatment covariates / solution;  
  lsmeans treatment / diff cl;  
  ods output Diffs=lsdiffs LSMeans=lsm solutionF=Parms;  
  by _Imputation_ ;  
run;
```

4. Combine estimates from the results of each of the 200 ANCOVA runs using SAS PROC MIANALYZE.

Sample SAS code:

```
PROC MIANALYZE parms(classvar=full)=lsdiffs;  
  class treatment categorical covariates;  
  modeleffects treatment;  
  ods output ParameterEstimates=MIAN_ lsdiffs;  
run;
```

Report the results of the least-squares mean estimates of the change from baseline in hemoglobin during the evaluation period, the estimates of treatment effect (e.g. least-squares mean CFB in

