23 APPENDIX 7: TEMPEROAL PROFILE OF TEAE'S OF SPECIAL INTEREST

24 APPENDIX 8: INVERSE PROBABILITY CENSORING WEIGHTED MODEL**Background**

Differential dropouts between treatment arms with informative censoring, may cause biased results from conventional survival methodology using Cox regression or other non-parametric survival analysis methods. The inverse probability of censoring weighted (IPCW) approach can be used under these situations to better estimate the treatment difference.

IPCW is an analysis method of time-to-event endpoint adjusting time-dependent variables as covariates and contribution of subjects in the analysis model using the inverse of their censoring probability. The basic idea of using this IPCW estimator is to correct for time-variant censored subjects by giving more weight to subjects who are not censored. This way, the final survival analysis model is fit as if censoring is absent. Subjects carry more weight in the analysis model if subjects stay longer in the trial, in other words, subjects who are censored sooner are less representative in IPCW estimators

Step 1: Model the censoring mechanism.

In the censoring model, the event of interest is censoring, hence the subjects who are lost to follow-up have an 'event'. Subjects that are not censored, i.e. those who experience the original event of interest, are now considered 'censored' since their censoring time is not observed. The probability of being censored will be estimated.

Step 2: Estimate the Product-Limit estimator and Cox proportional hazards estimator

Estimate the P-L estimator and Cox regression estimators using time to censoring for each subject j at each time point t , $K^0_j(t)$ and $K^Z_j(t)$. The Cox Model will include eGFR categories (eGFR ≤ 10 , $10 < \text{eGFR} < 15$, $15 < \text{eGFR} < 30$, and $\text{eGFR} \geq 30$), and Dialysis initiation (Yes, No) as time varying covariates. Covariates including baseline hemoglobin, and other randomization stratification factors will also be included in the model.

Step 3: Calculate the unstablized and stabilized IPCW (SIPCW) weights for each of the subjects, j , $W_{\text{unstab}_j}(t) = 1 / K^Z_j(t)$, $W_{\text{stab}_j}(t) = K^0_j(t) / K^Z_j(t)$.

Step 4: Estimate the survival and/or Cox model for time-to-event in the absence of censoring with the IPCW weight, SIPCW.

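### The US primary imputation model uses eGFR only as below or above 30, while the ANCOVA adjusts for measured baseline eGFR; adding the measured value is a free improvement

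*SAP*

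**What the plan says.** SAP Section 12.1 sets out the US primary analysis as multiple imputation followed by ANCOVA on the Weeks 28 to 52 mean change in Hb.

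- **Step 1, intermittent gaps:** an "imputation model with treatment, baseline hemoglobin, randomization stratification factors, and the available non missing hemoglobin for each scheduled Week". The sample code reads "var treatment covariates Week1 ... Week 52", run by treatment, and does not define its covariate placeholder.
- **Step 2, values after dropout:** "The regression imputation model includes an intercept and the slopes of the hemoglobin from previous Weeks and the stratification factors". For the first visit: "Missing data at Week 1 will be imputed using the regression imputation model with baseline stratification factor, baseline and hemoglobin from Week 1".
- **ANCOVA:** "The model will contain terms for baseline Hb and baseline eGFR measurements as covariates". The screening Hb and eGFR stratification factors are left out of this model; the other factors stay.

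Protocol Section 4.2 and SAP Section 3.2 define the eGFR factor as below 30 versus 30 or above (mL/min/1.73 m²). SAP Section 5.4 adds: "Randomization stratification factors derived from actual data (not the ones from the randomization system) will be used in all applicable analysis models". That changes the source of the factors but not their levels. The same section derives baseline eGFR as the mean of all central laboratory values before the first dose, so the measured value is available.

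**The concern.** An imputation model should normally contain every covariate of the analysis model. Here it holds a two-level version of a variable that the ANCOVA uses as measured. Given arm, stratum and earlier Hb, imputed Hb has no further relation to eGFR, whereas observed Hb may have one.

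This matters if baseline eGFR predicts both dropout and later Hb beyond those variables. The primary analysis would then be conditioning on too little for its missing-at-random assumption, and dropouts would be imputed as if they had the eGFR of those who stayed in their stratum. The SAP gives some reason to expect this. Section 13.1.2 suspects that dropout differs between arms. Appendix 8 says of its censoring model that "The Cox Model will include eGFR categories", with cuts at about 10, 15 and 30, so it allows for variation inside the lower stratum. At stake is a small error in the estimated difference and its interval.

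**Working it through.** **1. eGFR across the Hb models in the SAP**

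| Place | Form of eGFR |
|---|---|
| 12.1 step 1 (gaps) | two-level factor |
| 12.1 step 2 (after dropout) | two-level factor |
| 12.1 step 3 (ANCOVA) | as measured |
| 12.2.1 (MMRM sensitivity) | as measured |
| 12.2.4 (logistic, Hb response) | as measured, continuous |

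The Cox models for rescue and transfusion (Section 12.3, items 6 and 9) also adjust for baseline eGFR separately from the other stratification factors. The imputation steps are out of line with the rest of the plan.

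**2. When it biases the result**

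In arm a, let p_a be the share of evaluation-period Hb that is imputed, β_a the slope of later Hb on eGFR given stratum and Hb history, and d_a the mean eGFR of those observed minus that of dropouts, given the same. Roughly, imputed Hb is too high by β_a × d_a, and

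bias of the difference ≈ p_R β_R d_R − p_P β_P d_P (R roxadustat, P placebo).

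This is zero if the slopes are zero, if eGFR has no further link with dropout, or if the two terms cancel. With positive slopes, lower eGFR among dropouts and more placebo dropout, it is negative, toward the null. The opposite pattern would reverse the sign.

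**3. The plan's own power figure**

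Inputs from SAP Section 5.1: 300 versus 150, difference 0.75 g/dL, SD 1.2, two-sided 0.05.

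- SE = 1.2 × √(1/300 + 1/150) = 0.12
- 0.75 / 0.12 = 6.25; power = Φ(6.25 − 1.96) = Φ(4.29) = 99.999%

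The stated figure of more than 99% reproduces.

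**4. Size of the bias, by simulation**

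The documents give none of the inputs needed, so these are assumptions:

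- median eGFR 18, with 80% below 30
- Hb complete to Week 52 in about 45% of placebo and 80% of roxadustat subjects
- dropout hazard ratio 1.3 or 1.8 per 10 mL/min lower eGFR, with dropout also depending on the last Hb
- placebo Hb at Week 52 lower by 0 to 0.6 g/dL per 10 mL/min lower eGFR, with the roxadustat slope either zero or equal to placebo

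Hb was imputed sequentially within arm as in step 2, using baseline Hb and its stratum, earlier Hb and eGFR. The ANCOVA used continuous baseline Hb and eGFR. Bias is against the full-data estimate at N = 200,000. Imputation was by predicted mean, so this bears on the point estimate only. Each row spans four settings.

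| Placebo slope (g/dL per 10 mL/min) | Full-data difference | Bias, two-level eGFR | Bias, continuous eGFR |
|---|---|---|---|
| 0 | 1.596 to 1.605 | -0.005 to 0.002 | -0.005 to 0.002 |
| 0.15 | 1.590 to 1.605 | -0.014 to -0.002 | -0.001 to 0.004 |
| 0.3 | 1.575 to 1.604 | -0.028 to -0.009 | -0.001 to 0.002 |
| 0.6 | 1.547 to 1.606 | -0.053 to -0.016 | -0.002 to 0.002 |

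A second simulation, with 400 versus 200 subjects, about 18% versus 35% missing by Week 52 and proper imputation draws, gave -0.004 to -0.033 with strata only and 0.001 to 0.003 with eGFR added on the log scale.

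**5. Against the design**

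- Largest bias over design difference: 0.053 / 0.75 = 7%. Over the simulated effect: 0.053 / 1.55 = 3%.
- In units of the unadjusted complete-data SE: 0.053 / 0.12 = 0.44 at 300/150. At 800/400 the SE is 1.2 × √(1/800 + 1/400) = 0.073, and the ratio is 0.72.
- Taking the whole bias off the design difference: (0.75 − 0.053) / 0.12 = 5.81, and Φ(5.81 − 1.96) = Φ(3.85), still above 99.9%.

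**The case against.** The strongest reply is that the effect is negligible and rests on chosen inputs. That stands in part. With zero slope there is no bias, and the largest value needs about 55% of placebo subjects without Hb at Week 52 together with the steepest slope. All the simulated bias attributable to coarse eGFR points toward the null, so these results give no sign of a false positive claim.

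The MMRM sensitivity analysis uses measured eGFR in the ITT population and sits beside the primary result in SAP Table 4. This is a fair partial check. It is partial because no eGFR-by-visit term is listed, and because a gap between the two methods would not show which feature caused it. The pattern-mixture analyses vary the dropout assumption, but their described distribution covers Hb only.

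The undefined placeholder in the sample code could be meant to include measured eGFR. The prose lists in both steps do not include it; if it was intended, one line settles the matter.

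A reader might infer more than the documents support:

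- **That imputed Hb ignores eGFR.** It is coarsened, and earlier Hb carries part of any eGFR effect. Only the remainder is lost.
- **That missing at random fails.** It would hold if eGFR had no further link with later Hb, or none with dropout. The documents settle neither.
- **That the SAP's own dropout model proves the need.** Appendix 8 serves time to rescue and time to transfusion, where Section 12.3 leaves the choice between it and Cox open. Its categories are time-varying and paired with dialysis initiation. Section 13.1.2 concerns safety event rates.
- **That the eGFR ≤15 subgroup result (Section 14) is distorted.** The SAP does not say whether that analysis reuses the same imputed datasets.

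**Conclusion.** The mismatch is real: two-level eGFR in both imputation steps, measured eGFR in the ANCOVA. Its likely consequence is small, between 0 and about -0.05 g/dL under the assumed inputs, mostly toward the null, and removed by adding the covariate. The size and sign depend on dropout rates, the eGFR distribution and the eGFR-Hb slope, none of which the documents state. The primary conclusion is not at risk; what improves is the accuracy of the estimate and the agreement between imputation and analysis. This is an optional refinement.

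The Week 1 line is a separate drafting slip, since a missing value cannot predict itself. The closing sentence of step 2, which refers to previous weeks, makes the intent clear. The slip adds no weight to the eGFR point.

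**What to change.** In SAP Section 12.1, add baseline eGFR as a continuous covariate, on the same scale as in the ANCOVA, to the step 1 variable list and to the step 2 regressions, and spell out the covariate placeholder in the sample code. The ANCOVA states no transformation, so a log scale should be used in the imputation only if the ANCOVA also adopts it.

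Separately, state that missing Week 1 Hb is imputed from baseline Hb, baseline eGFR and the stratification factors.

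Cost: one already derived variable in the code and two sentences of text, with no new data. Both changes should be made before database lock, by which Protocol Section 9.5 requires the SAP to be final.

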7.1.2.4 Week 28 to End of Treatment (Every 4 weeks, ± 3 days)

- Laboratory tests (must be performed prior to next dosing cycle):
 - Week 28 followed by every 8 weeks: CBC with WBC differential
 - Week 28 followed by every visit where no CBC is collected: Hb only
 - Week 28 followed by every 8 weeks: Serum chemistry
 - Weeks 28, 36, 44, and 52 followed by every 12 weeks: Lipid panel (fasting whenever possible)
 - Week 28 followed by every 8 weeks: Serum iron, ferritin, TIBC, TSAT
 - Week 28 followed by every 8 weeks: CHr
 - Week 28 followed by every 16 weeks: HbA1c
 - Weeks 44, 68 and 84: Reticulocyte count
 - Weeks 44, 68 and 84: Special laboratory analytes (hepcidin, hsCRP)
 - Weeks 44, 68 and 84: Archival serum/plasma samples (optional donation, separate consent form)
- HemoCue assessment
- Week 36 followed by every 12 weeks: Targeted physical examination
 - Week 36 followed by every 12 weeks: Point of care qualitative urine pregnancy test for women of child bearing potential only
- Weeks 28, 52, and 76: 12-lead electrocardiogram
 - Dose adjustment review every 4 weeks (except/or more frequently in the event of excessive hematopoiesis). Refer to Section 2.1 and Appendix 1.
- All visit weeks: BP and B.
- All visit weeks: BP and heart rate
- Weeks 28, 52, and 76: HRQoL questionnaires (SF-36, FACT-An, and EQ-5D-5L)
- Adverse event recording
- Concomitant medication recording

- Procedures and nondrug therapy recording
- Dispense study drug (4 weeks supply), except at End of Treatment

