8 ENDPOINTS AND ASSESSMENTS

8.1 Primary Efficacy Endpoint

There are two separate regionally-based primary efficacy endpoints in this study depending upon whether the data are being filed to support submission to the US FDA or to Ex-US health authorities, such as the European EMA.

The **primary endpoint for the US (FDA)** submission is defined as the change in Hb from baseline to the average level during the evaluation period (defined as Week 28 until Week 52).

The **primary endpoint for the Ex-US** submission is defined as the proportion of subjects who achieve a Hb response at two consecutive visits during the first 24 weeks of treatment, without rescue therapy (ie, RBC transfusion, ESA, or IV iron)

A Hb response is defined, using central laboratory values, as the following:

- Hemoglobin ≥ 11 g/dL and Hb increase from baseline by ≥ 1 g/dL in subjects with baseline Hb > 8 g/dL, or
- An increase in Hb by ≥ 2 g/dL in subjects with baseline Hb ≤ 8.0 g/dL

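### The sample code for the FDA primary ANCOVA names `change_Week36` as its response, which contradicts the Weeks 28–52 mean that the text requires

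*SAP*

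**What the plan says.** SAP 12.1 defines the per-patient FDA endpoint as "Hb change from baseline to the average level during the evaluation period, defined as Week 28 to 52 of the treatment period". Both hypotheses in that section refer to the same average. Protocol 8.1 agrees: the endpoint is "the change in Hb from baseline to the average level during the evaluation period (defined as Week 28 until Week 52").

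SAP 12.1 then lists the steps of the primary analysis. Step 3 fits an ANCOVA to each imputed dataset "using the mean of all observed or imputed Hb values within the evaluation period". Directly below, under the label "Sample SAS code", the PROC MIXED block contains "model change_Week36 = treatment covariates / solution". After step 4 the instruction is: "Report the results of the least-squares mean estimates of the change from baseline in hemoglobin during the evaluation period".

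The name `change_Week36` appears only in that block and is not derived or defined elsewhere in the SAP.

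**The concern.** The sentence and the code in step 3 specify different responses for the test of the FDA primary hypothesis. Elsewhere in the block, items to be filled in are marked generically (`xx`, `covariates`). `change_Week36` is not generic: it names one week. It also stands among steps that fix two seeds and 200 imputations, detail whose purpose is that another programmer can reproduce the result.

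If the response were coded as named, three things would follow.

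- **The quantity estimated would change.** SAP 12.1 justifies the evaluation period by the longer-term effect that averaging to Week 52 captures. A Week 36 response carries nothing from Weeks 40 to 52.
- **The error could spread.** SAP 12.2 repeats the primary analysis in ITT2, PPS and FAS. The pattern-mixture analyses in 12.2.2 refit the ANCOVA, and 12.2.3 repeats the analyses with Hb censored after rescue. Item 4 of 12.3 borrows the FDA primary method for its by-frequency comparison.
- **The code would not clear up a related loose end.** Protocol 9.4.3.1 and SAP 12.3 item 2 list visit and treatment-by-visit terms for the MI ANCOVA, whereas step 3 of SAP 12.1 uses one mean per subject. The code is where a reader would look for the answer, and it gives a further version.

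**Working it through.** **1. Setting the passages side by side**

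| Place | Response |
|---|---|
| Protocol 8.1 and 9.4.3.1 | Change to the Weeks 28–52 average |
| SAP 4.1 | Same |
| SAP 12.1, endpoint and hypotheses | Same |
| SAP 12.1, step 3 sentence | Mean of observed or imputed Hb in the evaluation period |
| SAP 12.1, step 3 code | `change_Week36` |
| SAP 12.1, reporting sentence | Change during the evaluation period |

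One line differs from all the rest.

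**2. Visits in the evaluation period**

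Protocol 7.1.2.4 schedules visits every 4 weeks from Week 28, with Hb at each (in the CBC or alone). That gives Weeks 28, 32, 36, 40, 44, 48 and 52, so k = 7. A literal Week 36 response would leave six of the seven out of the outcome.

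**3. The plan's own power figures**

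Inputs from SAP 5.1: 300 vs 150 subjects, difference 0.75 g/dL, SD 1.2 g/dL, two-sided alpha 0.05.

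- SE = 1.2 × √(1/300 + 1/150) = 0.120, and 0.75/0.120 = 6.25. Power is 99.999%, against more than 99% stated. With the 1 g/dL of Protocol 9.1 it is higher still.
- 35 vs 150: SE = 1.2 × √(1/35 + 1/150) = 0.225. Power is 91%, against 90% stated.

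Both reproduce.

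**4. Week 36 alone against the seven-visit mean**

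Assumptions not in the documents: the name is literal, visit variances are equal, and any two visits have common correlation ρ (after adjustment for covariates). Imputation variance is ignored. Then

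Var(mean)/Var(single visit) = (1 + 6ρ)/7, and the SE ratio, single to mean, is 1/√[(1 + 6ρ)/7].

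The SAP does not say whether 1.2 is the SD of a single visit or of the mean. The reading less favorable to Week 36 takes it as the SD of the mean, so that the single-visit SD is 1.2 × ratio. Power is for 0.75 g/dL, from the noncentral t.

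| Assumed ρ | (1 + 6ρ)/7 | SE ratio | Single-visit SD | Power, 300 vs 150 | Power, 35 vs 150 |
|---|---|---|---|---|---|
| 0.3 | 0.400 | 1.58 | 1.90 | 97.6% | 55% |
| 0.4 | 0.486 | 1.43 | 1.72 | 99.2% | 64% |
| 0.6 | 0.657 | 1.23 | 1.48 | 99.9% | 77% |
| 0.8 | 0.829 | 1.10 | 1.32 | 99.99% | 85% |
| 0.9 | 0.914 | 1.05 | 1.26 | 99.997% | 89% |

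With first-order autoregressive correlation of 0.5 between adjacent visits, the ratio is 1.70 and pooled power 95.7%, the lowest value found. Pooled power falls below 99% only when the single-visit SD exceeds about 1.75. If 1.2 is instead the single-visit SD, Week 36 alone has the stated power and the mean does better.

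**5. A case in which Week 36 is not noisier**

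Let the SD rise linearly by 30% from Week 28 to Week 52. Relative to Week 28, the SD at Week 36 is 1.10. The SD of the seven-visit mean is 1.10 at ρ = 0.9 and 1.125 at ρ = 0.95. The usual gain from averaging has then gone.

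**The case against.** The strongest reply is that nothing prespecified is affected. The block is labelled as a sample and cannot run until the dataset and covariates are filled in. Elsewhere in SAP section 12, code is introduced as only similar to what will be run. The correct response is named in the sentence directly above the block, step 1 carries Hb through Week 52, and step 2 imputes to the end of the evaluation period. All of this stands, and it limits the point to a wrong line of code.

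Three stronger readings are tempting, and the documents support none of them.

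- A reader might infer that the plan has two candidate primary analyses. Every operative statement gives the Weeks 28–52 average, and an undefined variable in illustrative code does not create a second one.
- A reader might take it as settled that `change_Week36` is a single visit. It may be a leftover label for a Weeks 28–36 average, an interval used in SAP 12.3. Neither reading can be confirmed, and the comparison with one visit depends on the literal one.
- A reader might infer that the coded analysis is necessarily noisier. That is the usual result, but step 5 of the working shows an exception, and its size rests on quantities the plan does not state.

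What the reply does not remove is that the line names a specific response, the response is wrong, and no sentence says that text overrides code.

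**Conclusion.** The point holds as an internal contradiction in the specification of the FDA primary analysis. It does not put the prespecified endpoint in doubt, and it does not change the design power. The risk is in execution: a response coded as named would estimate a different quantity, and the error could carry into the analyses that reuse the ANCOVA.

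The loss of precision is conditional: a standard error about 1.1 to 1.4 times as large for ρ from 0.8 to 0.4, given a literal Week 36 and equal variances. Pooled power was about 96% or more in every scenario tried. A material loss of power appeared only in the 35 vs 150 calculation for individual dosing frequencies, and only if 1.2 g/dL is the SD of the mean. The case for correction rests on the estimand and on reproducibility, not on power of the pooled test.

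**What to change.** In SAP 12.1 step 3:

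- Replace `change_Week36` with a response named for the evaluation period. Define it as the per-subject mean of observed or imputed Hb at Weeks 28, 32, 36, 40, 44, 48 and 52, minus baseline Hb, computed within each imputed dataset.
- Add a sentence that the text governs wherever it differs from sample code.

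The cost is one line of code, one line of derivation and one sentence. Sample size, data collection and the hypothesis tested are unchanged. The edit should be made before unblinding.
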